## **BACKGROUND:**

Many women Veterans are of reproductive age and, of those, a substantial number experience mental health concerns. Women Veterans with mental illness are at greater risk for unplanned pregnancy and adverse pregnancy outcomes due to factors unique to mental illness and mental health treatment. In addition, mental health and mental health-related concerns associated with pregnancy (e.g. impact of pregnancy on mental health, psychiatric medication use during pregnancy) often affect reproductive life decisions and health outcomes. For these reasons, reproductive life planning (RLP), setting personal goals and plans regarding reproductive intentions, that incorporates considerations and addresses concerns specific to mental health conditions is particularly important for women with mental illness. Despite this need, women Veterans with mental illness rarely receive RLP, and current tools do not adequately consider or address the unique reproductive health considerations women with mental illness often experience.

Research on the efficacy of RLP in improving reproductive outcomes in and tailoring for women with mental illness is limited. Use of RLP in routine care and RLP interventions that specifically address the unique needs of women Veterans with mental illness are even more lacking. Both represents significant gaps that hamper the VHA's ability to provide quality comprehensive health care for women Veterans—gaps highlighted by the identification of reproductive mental health as a priority goal in the VHA's Strategic Plan for Enhancing Delivery of Reproductive Health Services and in the Women's Health Research Agenda. The current study attempts to address these gaps by examining the feasibility, acceptability, and potential efficacy of a mental health-informed facilitated RLP/RLP goal setting intervention specifically designed for women Veterans with mental illness (Reproductive Life Plan for Mental Health; RLP-MH).

## **METHODS:**

**Overview:** We will conduct a pilot feasibility trial of 40 women Veterans of reproductive age with mental illness receiving outpatient mental health services at the VA Maryland Health Care System (VAMHCS). Participants will be randomly assigned to 1) the RLP-MH intervention or 2) control (receipt of the VA's Reproductive Life Planning Quick Guide and other written materials) after completion of the baseline assessment. The purpose of this pilot trial is to establish feasibility and acceptability of the RLP-MH and to explore its potential efficacy.

**Participants:** Forty participants will be recruited from VAMHCS outpatient mental health and women's health programs (Baltimore & Perry Point VAMCs; CBOCs). Inclusion criteria are: (1) female, 2) between 18 and 40 years of age, (3) chart diagnosis of schizophrenia or schizoaffective disorder, bipolar disorder, major depression, or PTSD, and (4) currently receiving mental health services at the recruitment site. Exclusion criteria are: (1) currently pregnant, or (2) inability to have children (e.g. infertility, hysterectomy, tubal ligation).

**Recruitment:** Recruitment will take place at outpatient clinics/programs within the VA Maryland Health Care System (VAMHCS). Potential VA participants will be identified by several methods: (1) CPRS chart review and screening via use of a partial HIPAA waiver, (2) VA clinician referrals of participants who meet inclusion criteria and who might be interested in participating, (3) Self referrals by participants who hear about the study and are interested in participating or who have participated in other MIRECC studies and have given permission to be contacted regarding future studies, (4) Self-referral via IRB approved study flyer and other advertisements. Per VA requirements, initial contact with potential veteran participants will be made in person or by letter prior to any telephone contact. Specifically, we will approach individuals before or after their VA appointments.

We may also send out a letter to potential participants to see if they are interested in participating in the study. In this letter, they will be given contact information for the study staff (phone number) as well as a pre-stamped postcard to mail back to indicate their interest or lack of interest in the study. If after a few weeks, we do not hear from them, a follow-up phone call may be made to ensure the potential participant received the mailing. This follow-up phone call is mentioned in the mailing, so that potential participants will not be caught off guard when they receive a call from study staff.

We will use VA email to communicate with potential and current participants in order to send electronic copies of resources, blank worksheets, and/or response cards for them to use at a later time. We will only 1) contact potential veteran participants via VA email at their request after they have provided and given us permission to contact them via email or 2) send study materials at the veteran's request (staff will discuss proper procedures for communication via email with the veterans ahead of time to ensure understanding). The emails will also include a clear statement that no completed forms or personal identifying information should be sent to staff via email correspondence.

Research staff will email or mail potential Veteran participants a copy of the informed consent form and then meet with the potential Veteran participants by phone or via telehealth. We will use the following procedures outlined below to review to consent document and ensure that the participant is fully informed prior to providing verbal consent (we will not collect informed consent forms signed by the participant).

The study interviewer will provide an overview of the project, and invite him/her to participate. Interested participants are provided an informed consent form. After the consent form has been summarized in detail and all questions answered, the staff confirms that the participant is still interested in participating by soliciting a verbal response. Those who express willingness to provide consent must complete a brief questionnaire to assess competency and understanding of the consent form. If the participant is unable to answer the questions correctly, staff re-reviews the aspects of the study that the participant did not understand. The staff member asks the questions a second time. If the participant cannot answer all questions correctly, he/she will not be enrolled in the study. Participants will also receive a Health Insurance Portability and Accountability Act Authorization to Obtain, Use and Disclose Protected Health Information for Research (HIPPA) that will be reviewed with them. Staff will ask participants if they have any questions once the document has been read.

#### **Procedures:**

**Baseline Assessment:** Women Veterans who consent to participate will complete a baseline assessment. Research assistants conducting the baseline interviews will be blind to the participant's condition. After the assessment is completed (~45-60 min), the Veteran will be randomized to one of the two study conditions by the study interventionist 1) the RLP-MH intervention (a RLP-MH session and 1-month follow-up phone session) or 2) the control (written materials on reproductive life planning).

#### **Study Interventions:**

##### **RLP-MH condition:**

RLP-MH session: Those who are assigned to the RLP-MH intervention condition will complete the RLP-MH session after baseline. Sessions will be completed using telehealth. During this session, participants will meet with the RLP facilitator to complete the RLP-MH tool and develop a reproductive life plan. This will involve discussing whether the participant wants to have children, number and timing of pregnancies, physical and mental health conditions and

behaviors that may impact pregnancy, planned method of contraception if the participant does not want to get pregnant immediately, and potential action steps related to the reproductive life plan. Once all relevant components of the RLP-MH are completed, the facilitator and participant will develop a brief personal RLP summary (~4-5 sentences long) that summarizes the individual's reproductive life plans and goals. The final RLP summary, action steps, and obstacle-minimizing strategies will be recorded on the RLP Goals Worksheet and a copy given to the participant either in person or via mail if being completed via telehealth. Their RLP summary and goals will also be entered into a chart note with providers chosen by the participant included as co-signers. This session will take approximately 45-60 min to complete. Immediately after completing their RLP summary and goals, participants will be asked to complete a brief post-treatment assessment (~15 minutes; RLP-MH condition participants only). For appointments conducted over telehealth, participants will be sent a link to the questionnaires via by email or text.

**One-month Follow-Up Session:** The RLP-MH facilitator will conduct a brief follow-up session in-person or by phone (depending on the individual's preference) ~ one month after completing the RLP-MH session to discuss progress in addressing RLP goals and problem-solve around any obstacles to addressing goals. This session will last ~ 15 minutes.

**Control Condition:** Those that are assigned to the control condition will received written materials on reproductive life planning and information on VA resources for women Veterans. The facilitator will briefly review these materials with the participant, including a brief description, potential purpose/benefit, how they might be used, and how a RLP can be shared with provider(s). Review of these materials will take approximately 15 minutes. This intervention can be done via telehealth, or over the phone, depending on the participant's availability following randomization. Participants will either be emailed or mailed the corresponding materials, depending on their preferences, prior to reviewing the materials.

**2-month Follow-up Assessment:**

Research staff will attempt to contact participants by phone and/or by letter in order to schedule the 2-month post-treatment assessment. Follow-up interviews will be completed either in person or via telephone and will last approximately 45-60 min.

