**STATISTICAL ANALYSIS PLAN:**

Overview: Consistent with the objectives of this small pilot randomized controlled trial (RCT), our primary data analysis approach will be to estimate means, proportions, and group differences with point and interval estimation (i.e. 95% confidence intervals). In the face of sample variation, a confidence interval provides a range for the "true" population value of a parameter consistent with the observed data. Further, estimates of recruitment, completion, and attrition percentages will be used to plan for a larger trial if warranted. We will estimate difference of means (and effect sizes) and proportions on outcomes to evaluate potential for efficacy as another input to the decision whether the RLP-MH intervention merits further testing. The trial will be conducted according to the "intent-to-treat" principle in that outcomes will be assessed regardless of RLP-MH attendance.

**Aim 1 - Feasibility:** We will calculate point and interval estimates of the overall recruitment percentage and the RLP-MH intervention completion percentage (defined as attending baseline visit and the one-month follow-up visit). The point estimate for overall recruitment percentage = number consented / number approached to participate in the trial. Interval estimation will be by 95% confidence intervals. The point estimate for the RLP-MH completion percentage = number completed / number randomized to the intervention. The overall and group attrition percentages

will also be estimated, = number without the 2-month assessment / number consented and randomized. Interval estimation will be by 95% confidence intervals. In addition to assessing feasibility, these estimates will also inform the planning of a subsequent confirmatory trial if warranted. Point and interval estimates will be calculated to estimate mean fidelity score to further assess feasibility.

Aim 2 – Acceptability: Acceptability of the RLP-MH intervention will be assessed quantitatively and qualitatively. Quantitatively, we will calculate point and interval estimates of our satisfaction questionnaire. Responses to open-ended acceptability questions at the post-treatment assessment will be compiled and examined for common themes.

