Aim 3 – Explore Potential Efficacy: Preliminary. Before we perform analyses, we will first check variable distributions and missing data. Despite randomization, with a smaller sample size it is possible for covariate imbalance to occur by chance. As a sensitivity analysis, when making group comparisons, if a clinically relevant covariate (e.g. age, race) significantly differs across the two conditions we will repeat the primary analysis adjusting for the covariate to assess its impact on outcome effects as a secondary analysis.

3a: For the three outcomes for this sub-aim, the Decisional Self-Efficacy, Attitudes Towards RLP, and RLP Behavioral Intentions scales we will estimate the difference in mean change from baseline to the 2-month follow-up between the RLP-MH and control groups using a simple random intercept linear mixed model. This will allow inclusion of all observed outcome data. Between-group effect sizes will be calculated as the model-estimated difference in mean change divided by baseline pooled (across interventions) raw standard deviation. A bootstrap procedure will be used for effect size interval estimation. In addition to the comparisons between groups above, we will estimate the mean change in the RLP-MH condition on the RLP Behavioral Intentions and Decisional Self-Efficacy Scales from baseline to post-intervention using a mixed model.

3b: The RLP behaviors that will be quantitatively analyzed are generally Yes/No self-report questionnaire items that will be assessed at the 2-month follow-up in both arms of the trial. For example, questions ask: (1) if they've had any patient-provider reproductive health discussions, (2) if they've sought after reproductive health information, and (3) if they've taken any steps to address their reproductive needs or goals. We will estimate the group difference in the proportion of 'Yes' responses with point and interval estimates using normal approximation. To adjust for a potential out-of-balance covariate (e.g. race) we will use logistic regression.

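### Does the undefined start of the 2-month assessment give the RLP-MH arm an extra month to report reproductive health behaviors?

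*Combined protocol and SAP*

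**What the plan says.** The 2-month Follow-up Assessment paragraph tells staff to contact participants "in order to schedule the 2-month post-treatment assessment". It gives no start event and no visit window.

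Under RLP-MH condition, right after the first session, "participants will be asked to complete a brief post-treatment assessment". The one-month session is then timed from that first session. The Procedures section describes the active arm as "the RLP-MH intervention (a RLP-MH session and 1-month follow-up phone session", and Aim 1 of the SAP counts completion as "defined as attending baseline visit and the one-month follow-up visit".

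Control is a single contact: "Review of these materials will take approximately 15 minutes". Its mode depends on the participant's "availability following randomization".

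The SAP Overview states that "outcomes will be assessed regardless of RLP-MH attendance". The Aim 3b behaviors are Yes/No items "assessed at the 2-month follow-up in both arms of the trial". Their recall period is not shown.

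**The concern.** *Post-treatment* could mean after the first session or after the whole intervention. If the intervention includes the one-month session, treatment ends about a month later in RLP-MH than in control. A 2-month assessment counted from that point would give RLP-MH women about half as much time again in which to talk to a provider, look for information or take a step toward a goal. If the items ask whether the behavior has ever happened since enrollment, more time means more Yes answers with no intervention effect. The Aim 3b differences feed the decision on whether RLP-MH merits further testing, so an artifact in them would matter.

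A second worry does not depend on the reading. Outcomes are to be assessed whatever the attendance, yet a woman who attends no session has no treatment date to count from. Counted from the one-month session, a woman who misses only that session would have none either.

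**Working it through.** **1. What the term means elsewhere in the documents**

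| Place | Use | Points to |
|---|---|---|
| RLP-MH condition | post-treatment questionnaire given straight after the RLP summary and goals | first session |
| SAP, Aim 2 | open-ended acceptability answers collected at the post-treatment assessment, apparently the same one | first session |
| SAP, Aim 3a | RLP-MH change up to a point labeled post-intervention; the only intermediate assessment described is the one after the first session | first session |
| One-month Follow-Up Session | one month counted explicitly from the first session | first session as time zero |
| Procedures; SAP, Aim 1 | one-month session counted as part of the intervention and of completion | later end of treatment, but as content and attendance, not as the timing of an assessment |

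No section uses the term for a time after the one-month session. Counting from that session would also put a visit named for 2 months about 3 months after the first session.

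**2. Length of the windows, from first contact to assessment**

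- Counted from the first session or control contact: 2 months in each arm, gap 0.
- Counted from the end of the full intervention: 1 + 2 = 3 months in RLP-MH and 0 + 2 = 2 months in control, gap 1 month.

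**3. The plan's own precision**

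Sample size considerations gives intervals for .25 vs .10, .50 vs .20 and .60 vs .20. With half-width = 1.96 × √[p₁(1−p₁)/n + p₂(1−p₂)/n] and n = 20 per arm:

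- .25 vs .10: 1.96 × √(.009375 + .0045) = .231, interval (−.08, .38)
- .50 vs .20: 1.96 × √(.0125 + .008) = .281, interval (.02, .58)
- .60 vs .20: 1.96 × √(.012 + .008) = .277, interval (.12, .68)

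These match the printed intervals. The text says they allow for 15% attrition, but they match at 20 per arm, not 17. At 17 the half-widths are about .25, .30 and .30. That is a separate matter, and it only widens the yardstick used here.

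**4. Size of the artifact on the less natural reading**

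Assume open-ended recall and no intervention effect. Let p₂ be the 2-month proportion, taken from the plan's control values of .10 and .20. Let r be the third-month event rate relative to the first two months. The documents give no event rate over time, so r is an assumption, shown from 0 to 1.

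Monthly rate h = −ln(1−p₂)/2, and p₃ = 1 − (1−p₂) × exp(−r × h).

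| p₂ | r = 0 | r = .5 | r = 1 |
|---|---|---|---|
| .10 | .100 (+0) | .123 (+.023) | .146 (+.046) |
| .20 | .200 (+0) | .243 (+.043) | .284 (+.084) |

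At r = 1, .046/.231 = 20% and .084/.281 = 30% of the corresponding planned half-width.

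**5. Women without a session**

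Randomization follows the baseline assessment, so every randomized woman has a baseline date. Aim 3a already measures change from baseline. The documents do not say how many women are expected to attend no session. The completion scenarios of .60, .75 and .90 imply 20 × .40 = 8, 20 × .25 = 5 and 20 × .10 = 2 non-completers. These would lack an end-of-intervention date only if staff counted from the one-month session.

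**6. Would a fixed date from randomization be a clear gain?**

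If the first session takes place d months after randomization, the one-month contact falls at about d + 1. An assessment fixed at month 2 comes before that contact whenever d + 1 > 2, that is, d > 1. A recall stem running from baseline would also span the trial's own facilitator contacts, two in RLP-MH and one in control, and women might count these as discussions or information-seeking.

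**The case for a change.** The best case for a change is that one sentence would settle the matter. Every randomized woman is in the attrition denominator, so without a due date and window it is not strictly defined when an assessment is late or missed. Two staff members could read the term differently. Wide intervals do not excuse a bias in the point estimate, and the estimates inform the decision on further testing.

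Some of this stands. The start event is not written down, and a woman with no session has no explicit due date. The rest is weaker. The uses of the term that concern timing agree on the first session, so divergent practice is possible but not invited by the text. The artifact needs three things together: the less natural start point, open-ended recall that the documents do not show, and continued events in the third month. If any one fails, it is small or absent. The attrition point concerns how lateness is classified, and no bias in Aim 1 is shown. The obvious remedy also has costs: a date fixed from randomization can collide with the one-month contact when the session is late, and a recall stem from baseline could introduce an imbalance of its own.

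**Conclusion.** The concern does not call for a change. On the reading that the documents support, both arms are assessed about 2 months after their first contact, and the spurious Aim 3b difference is about 0, apart from unequal session delays. Only if staff counted from the one-month session, recall were open-ended and events continued at the same rate in month three would it reach about .05 (from .10) or .08 (from .20). These values rest on an assumed constant event rate and lie well inside the planned half-widths of .23 to .28 in an exploratory aim without a hypothesis test. The missing date for a woman who attends no session is a gap in wording. Baseline is available for every randomized woman and already serves as the origin of the Aim 3a change, so staff and analysts can fill the gap sensibly. How many women this would affect cannot be stated from the documents.

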**STATISTICAL ANALYSIS PLAN:**

Overview: Consistent with the objectives of this small pilot randomized controlled trial (RCT), our primary data analysis approach will be to estimate means, proportions, and group differences with point and interval estimation (i.e. 95% confidence intervals). In the face of sample variation, a confidence interval provides a range for the "true" population value of a parameter consistent with the observed data. Further, estimates of recruitment, completion, and attrition percentages will be used to plan for a larger trial if warranted. We will estimate difference of means (and effect sizes) and proportions on outcomes to evaluate potential for efficacy as another input to the decision whether the RLP-MH intervention merits further testing. The trial will be conducted according to the "intent-to-treat" principle in that outcomes will be assessed regardless of RLP-MH attendance.

**Aim 1 - Feasibility:** We will calculate point and interval estimates of the overall recruitment percentage and the RLP-MH intervention completion percentage (defined as attending baseline visit and the one-month follow-up visit). The point estimate for overall recruitment percentage = number consented / number approached to participate in the trial. Interval estimation will be by 95% confidence intervals. The point estimate for the RLP-MH completion percentage = number completed / number randomized to the intervention. The overall and group attrition percentages

will also be estimated, = number without the 2-month assessment / number consented and randomized. Interval estimation will be by 95% confidence intervals. In addition to assessing feasibility, these estimates will also inform the planning of a subsequent confirmatory trial if warranted. Point and interval estimates will be calculated to estimate mean fidelity score to further assess feasibility.

Aim 2 – Acceptability: Acceptability of the RLP-MH intervention will be assessed quantitatively and qualitatively. Quantitatively, we will calculate point and interval estimates of our satisfaction questionnaire. Responses to open-ended acceptability questions at the post-treatment assessment will be compiled and examined for common themes.

Aim 3 – Explore Potential Efficacy: Preliminary. Before we perform analyses, we will first check variable distributions and missing data. Despite randomization, with a smaller sample size it is possible for covariate imbalance to occur by chance. As a sensitivity analysis, when making group comparisons, if a clinically relevant covariate (e.g. age, race) significantly differs across the two conditions we will repeat the primary analysis adjusting for the covariate to assess its impact on outcome effects as a secondary analysis.

3a: For the three outcomes for this sub-aim, the Decisional Self-Efficacy, Attitudes Towards RLP, and RLP Behavioral Intentions scales we will estimate the difference in mean change from baseline to the 2-month follow-up between the RLP-MH and control groups using a simple random intercept linear mixed model. This will allow inclusion of all observed outcome data. Between-group effect sizes will be calculated as the model-estimated difference in mean change divided by baseline pooled (across interventions) raw standard deviation. A bootstrap procedure will be used for effect size interval estimation. In addition to the comparisons between groups above, we will estimate the mean change in the RLP-MH condition on the RLP Behavioral Intentions and Decisional Self-Efficacy Scales from baseline to post-intervention using a mixed model.

3b: The RLP behaviors that will be quantitatively analyzed are generally Yes/No self-report questionnaire items that will be assessed at the 2-month follow-up in both arms of the trial. For example, questions ask: (1) if they've had any patient-provider reproductive health discussions, (2) if they've sought after reproductive health information, and (3) if they've taken any steps to address their reproductive needs or goals. We will estimate the group difference in the proportion of 'Yes' responses with point and interval estimates using normal approximation. To adjust for a potential out-of-balance covariate (e.g. race) we will use logistic regression.

Sample size considerations: With an interval estimation approach, sample size is reflected in the precision of these estimates (i.e. the larger the sample the smaller the confidence interval widths). For example, for feasibility (Aim 1), with the proposed sample size of 20 randomized per study arm, observed intervention completion proportions in the RLP-MH group of .60, .75, and .90 would have 95% confidence intervals of (.39,.81), (.56,.94), and (.77,1.00). For potential efficacy assessed at the 2-month follow-up (Aim 3b), one assessed health behavior outcome will be "Any conversations with health provider regarding RLP or reproductive health? Yes/No". If the proportions of Yes responses to this question in the RLP-MH and control condition are, respectively, .25 and .10, .50 and .20, or .60 and .20, then the point estimates for the difference would be .15, .30, and .40, favoring RLP-MH, and the 95% confidence intervals for the differences would be (-.08,.38), (.02,.58), and (.12,.68). These calculations account for attrition equal to 15%.

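### The Aim 3 sensitivity adjustment hangs on a baseline significance test that, at 20 per arm, flags a continuous covariate only at an observed difference of about 0.64 SD

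*Combined protocol and SAP*

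**What the plan says.** The Preliminary paragraph of Aim 3 (Statistical Analysis Plan) recognises that a small randomized sample can be unbalanced by chance. Its remedy is that "if a clinically relevant covariate (e.g. age, race) significantly differs across the two conditions we will repeat the primary analysis adjusting for the covariate". The stated purpose is "to assess its impact on outcome effects as a secondary analysis", and the same sentence calls the run a sensitivity analysis. No test, significance level or imbalance size is given, and age and race are examples, not a closed list.

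Aim 3a estimates the between-group difference in mean change with a random-intercept linear mixed model. Aim 3b estimates a difference in proportions by normal approximation and adds: "To adjust for a potential out-of-balance covariate (e.g. race) we will use logistic regression". That sentence does not repeat the significance condition and does not define what counts as out of balance. The Preliminary rule nevertheless covers group comparisons in general.

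The Sample size considerations work "with the proposed sample size of 20 randomized per study arm". The SAP Overview makes estimation with 95% intervals the main approach and treats the Aim 3 estimates as one input to the decision on further testing.

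**The concern.** After randomization, a baseline p-value does not measure what this sensitivity analysis is for. In a simple comparison of means, an imbalance shifts the estimate by roughly the size of the imbalance times the strength with which the covariate predicts the outcome. The p-value ignores the second factor. It also judges the first against a threshold that is at its widest in small samples, which is the situation the paragraph worries about.

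Two things follow. A moderate imbalance in a predictive covariate will normally produce no adjusted analysis, and a reader may take its absence as reassurance. In addition, because the covariate list is open, which covariates are tested and adjusted for can be settled after the data are seen.

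**Working it through.** **Inputs.** From the SAP: 20 randomized per arm; 15% attrition, so 20 × 0.85 = 17 per arm at 2 months. Assumed, because the SAP is silent: two-sided 5% level, in line with its 95% intervals; imbalance cut-offs from 0.2 to 0.6 SD; covariate–outcome correlation of 0.3 to 0.5.

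**1. The plan's own figures.** The SAP gives no figure for the baseline test. Its completion intervals confirm the working size of 20 per arm. With p ± 1.96·√(p(1−p)/20):
- .60 gives (.385, .815)
- .75 gives (.560, .940)
- .90 gives (.769, 1.03, cut to 1.00)

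All three agree with the printed values.

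**2. Difference needed to trigger, continuous covariate.** The t-test has 38 degrees of freedom and critical value 2.024. Smallest flagged standardized difference = 2.024 × √(2/20) = 2.024 × 0.316 = 0.64 SD.

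**3. Share of chance imbalances not flagged.** Under randomization the observed standardized difference is distributed as t(38) × √(2/20). The test flags 5.0% of trials, all of them beyond 0.64 SD. For a cut-off T below 0.64, the share missed is 1 − 0.05/P(|d| > T).

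| T (SD) | P(\|d\| > T) | Share missed |
|---|---|---|
| 0.2 | .531 | 91% |
| 0.3 | .349 | 86% |
| 0.4 | .214 | 77% |
| 0.5 | .122 | 59% |
| 0.6 | .065 | 24% |

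At 0.4 SD, unflagged imbalances arise in .214 − .050 = .164 of trials, for one covariate.

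**4. Binary covariate.** For 5/20 against 11/20 the pooled proportion is 16/40 = .40. z = .30/√(.40 × .60 × 2/20) = .30/.155 = 1.94, so chi-square p = .053; Fisher's exact p = .105. Starting from 5/20, the other arm must reach 12/20 (chi-square) or 13/20 (Fisher) to be flagged.

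**5. What an unflagged imbalance can do.** For a simple difference in means, shift = correlation × imbalance, and SE = √(2/20) = 0.316 outcome SD.
- Imbalance 0.4 SD: shift 0.12 SD at correlation 0.3, 0.20 SD at 0.5.
- Imbalance just under 0.64 SD: shift 0.19 SD at 0.3 (about 0.6 SE), 0.32 SD at 0.5 (about 1.0 SE).

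**6. Whether adjustment would act in the planned models.** In 3a there are two time points. With complete data the group-by-time estimate is the difference in mean change, and a covariate that is constant over time cancels from each woman's change. A main effect alone therefore leaves the estimate where it was; only a covariate-by-time term can move it, and only if the covariate predicts change. In 3b there is no baseline measure in the analysis, so any relation between covariate and outcome carries through. The data may be thin, however: in the SAP's .25 against .10 scenario with 17 per arm, the expected number of 'Yes' responses is 17 × .25 + 17 × .10 = 4.25 + 1.70 = 5.95.

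**The case against.** The strongest reply is that little depends on this rule. The trial is a feasibility pilot, the adjusted run is secondary, and the trigger decides only whether an extra analysis is shown. Averaged over randomizations, the unadjusted interval keeps its nominal coverage. All of this stands. A reader might infer that the baseline test biases or selects the main Aim 3 result; the documents do not support that, because the unadjusted analysis is kept in every case.

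A reader might also infer that the rule misses some fixed share, say three quarters, of the imbalances that matter. That figure belongs to a cut-off near 0.4 SD, which the SAP does not set; the table above runs from 91% to 24%. Nor do the documents give a covariate–outcome correlation, so the shifts in step 5 are illustrations. For 3a they apply only as far as the covariate predicts change.

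The rule is restricted to clinically relevant covariates, so it is not an invitation to adjust for anything that reaches p < .05. But clinical relevance is not defined as predicting these outcomes, and the list is not closed. With only the two named examples tested, and taken as independent, the chance of at least one trigger is 1 − .95² = 9.8%. A much higher rate would require a longer list than the SAP gives.

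Finally, adjustment for everything has its own cost. In 3b, logistic regression moves the result from a difference in proportions to an odds ratio and may be unstable with about six 'Yes' responses. This is a fair limit on the remedy, not a defence of the trigger.

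**Conclusion.** The point holds as an inexpensive improvement to a secondary analysis. The 0.64 SD trigger rests only on 20 per arm and an assumed two-sided 5% level. The miss rates also need a chosen cut-off, and for continuous covariates more than half of chance imbalances are missed at any cut-off up to 0.5 SD. The harm is confined to the missing check: moderate imbalance will usually pass without an adjusted analysis, while the estimates are used in deciding whether to go further.

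A reader might expect fixed adjustment to bring a precision gain of the order of 5–13%, the value of 1 − √(1 − r²) for correlations of 0.3 to 0.5. That should not be claimed. The formula belongs to simple linear regression of an outcome on a covariate, not to the change model in 3a or the logistic model in 3b.

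**What to change.** Replace the conditional sentence in the Aim 3 Preliminary paragraph with a fixed rule:

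- **Covariates.** Name one or two now, chosen because they are expected to predict the Aim 3 outcomes and are already collected. Age is an obvious candidate: it is an eligibility criterion and the SAP already mentions it.
- **When.** Run the adjusted sensitivity analysis for the between-group comparisons in 3a and 3b whatever the baseline table shows. Describe balance by standardized differences, without p-values.
- **3a.** Enter each covariate with its covariate-by-time term.
- **3b.** Keep the unadjusted difference in proportions as primary. Where 'Yes' responses are few, adjust for one covariate only or use penalized (Firth) logistic regression. Replace the undefined out-of-balance condition with the same named covariates.

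The cost is a few sentences of SAP text, one or two model degrees of freedom (in 3a also those for the time terms), and possible instability in sparse 3b items, which the last provision is meant to contain. No new data are needed.
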